9.4 EVALUATING ADVERSE EVENTS

All AEs will be graded according to the CTCAE version 4.03.

9.5 ASSESSMENT OF CAUSALITY

Investigators are required to assess the relationship, if any, of each AE or SAE to the investigational drug using clinical judgment to determine the degree of certainty with which an AE can be attributed to the investigational drug. Alternative causes, such as natural history of the underlying disease, other risk factors, and the temporal relationship of the event to the administration of the study medication must be considered.

Relationship to study drug is summarized as follows:

- Not Related: There is another obvious cause of the AE
- Unlikely to be related: There is another more likely cause of the AE
- **Possibly related:** The AE could have been due to the investigational drug
- **Probably related:** The AE is probably attributable to the investigational drug

• **Definitely related:** The AE is most likely attributable to the investigational drug

9.6 REPORTING REQUIREMENTS

Any AE (with the exception of worsening AD symptoms or injection site reactions) of grade 2 or higher must be entered into the eCRF within 24 hours of learning of the event. Any grade 3 or greater injection site reaction must be reported to the sponsor within 24 hours of learning of the event.

All serious adverse events (SAEs) should be reported to the Sponsor within 24 hours of knowledge of the event. These immediate reports should be followed promptly by detailed, written reports. The subject should be followed up with until stabilization of the reported SAE, either with full satisfactory resolution or resolution with sequelae, or until death of the subject. Before declaring the subject is lost to follow-up, three unsuccessful attempts at contact should be made and recorded on the SAE form. The immediate and follow-up reports should identify subjects by unique code numbers assigned to the trial subjects rather than by the subjects' names, personal identification numbers, and/or addresses. The Investigator should also submit SAEs to the IRB/EC according to their IRB/EC guidelines [ICH-GCP E6]. Drug-related Serious Adverse Events will be reported to the FDA by XBiotech's Medical Safety Officer according to 21 CFR 312.32.

9.7 REFERENCE SAFETY INFORMATION: POTENTIAL ADVERSE REACTIONS

831 patients have been treated using bermekimab in patients with advanced solid tumors, advanced hematologic malignancies, metastatic colorectal cancer, peripheral vascular disease, type II diabetes, acne vulgaris, plaque psoriasis, and pyoderma gangrenosum. Over 1200 doses of bermekimab were administered at 7.5 mg/kg to refractory, metastatic CRC patients with cancer associated symptoms at baseline (ECOG performance status 1 and 2). In this trial (PT026), which is the largest controlled trial completed with bermekimab to date (N=309), patients were dosed at 7.5 mg/kg for metastatic colorectal cancer. The most common AEs reported (>10%) were abdominal pain, peripheral edema, fatigue, anemia, constipation, decrease in weight, asthenia, decreased appetite, and nausea. The majority of these events were grade 1 or 2 and appeared to be related to the underlying CRC. The prevalence of these events was similar in the bermekimab and placebo groups. Two infusion reactions were reported in this trial, and they were not serious or severe (grade I or II).

Bermekimab is a recombinant human IgG1 monoclonal antibody specific for human interleukin-1 α (IL-1 α). As such, it is an immunomodulator that has anti-inflammatory and anti-neoplastic properties. Other agents that could be considered in the same pharmacologic class include biologic agents that target IL-1 receptor antagonist and IL-1 beta. Potential risks for agents in this class include infusion or injection site reactions, particularly with respect to IL-1ra, although in this case is likely related to the unanticipated agonist effects of the receptor antagonist when it is present in high local concentration at the site of injection and thus this effect is not relevant to bermekimab.

Bermekimab is human monoclonal antibody derived immune plasma B cells derived from a natural human immune response against IL-1a. Unlike previous generations of humanized or fully human antibodies, the entire bermekimab heavy and light chain sequences are identical to those found in naturally-occurring human IgG1 κ , with the light and heavy chain variable regions being identical to those originally expressed by a peripheral blood B lymphocyte that was obtained from a healthy individual. No *in vitro* affinity maturation or modifications have been made to improve its natural binding affinity (211 +/- 31 pM). We believe that a true human antibody should be effectively non-immunogenic in humans and thus exhibit optimal activity and pharmacokinetics. To date, no treatment emergent anti-drug antibodies specific to bermekimab have been identified.

The mechanism behind infusion reactions is not clear in all cases. It may involve a reaction against the antibody, against excipients in the preparation such as polysorbate, or against some minor residual component from the manufacturing process (i.e. host cell proteins). To date, there has been a very low incidence of mild injection site or infusion reactions observed (20 patients out of 831 total; 2.4%). All except two of these patients had grade 1 or 2 reactions that did not result in discontinuation. In order to mitigate this class-specific risk, close monitoring is required during the bermekimab infusion and for at least 1 hour after infusion. Availability of resuscitation equipment must be ensured. *Pre-medication with antihistamines or corticosteroids is not required*.

For the purposes of expedited safety reporting in clinical trials, the following should be considered expected events:

- Infusion Related Reactions
- Injection Site Reactions

10. STATISTICAL PLAN

This section provides the basis for the statistical analysis plan (SAP) for the study. The SAP may be revised during the study to accommodate amendments to the clinical study protocol, and to make changes to adapt to unexpected issues in study execution and data that may affect planned analyses. Analysis variables are listed in Section 8.

10.1 STATISTICAL HYPOTHESIS

No formal hypothesis tests will be performed for the primary endpoints.

10.2 DETERMINATION OF SAMPLE SIZE

The sample size chosen was one of convenience, and no formal sample size calculations were performed.

10.3 ANALYSIS SETS

10.3.1 Safety Analysis Sets

The safety analysis set (SAF) consists of all patients that receive at least one dose of study medication and will be analyzed as treated.

The secondary endpoints will be analyzed based upon the SAF, as well as the per protocol population (PP). The per protocol population will consist of those patients that complete both the baseline and visit 8 assessments of their atopic disease (as specified for the secondary endpoints).

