- Change in SCORing Atopic Dermatitis (SCORAD) score from baseline to visit 8
- Patients (%) achieving 50% or greater reduction in EASI Score from baseline at visit 8
- Patients (%) achieving 50% or greater reduction in SCORAD Score at visit 8
- Change (%) in Patient Oriented Eczema Measure (POEM) Scores from baseline to visit 8
- Changes in Global Individual Signs Score (GISS) from baseline to visit 8
- Change from baseline to visit 8 in Dermatology Life Quality Index (DLQI)
- Change from baseline to visit 8 in Hospital Anxiety Depression Scale (HADS)

• Change (%) from pre- and post- injection of Visit 1 Questionnaire for pruritus, pain and erythema

Trial Design:

Phase 2, Open label, Dose Escalation Study of Bermekimab (MABp1) in Patients with Moderate to Severe Atopic Dermatitis.

Group A (n=9): patients will receive a total of 4 X 200mg subcutaneous injections of bermekimab. Dosing will occur weekly from visit 1 to visit 4.

Group B (n=20): patients will receive a total of 8 X 400mg subcutaneous injections of bermekimab. Dosing will occur weekly from visit 1 to visit 8.

Inclusion Criteria: No waivers/exemptions will be granted for protocol inclusion/exclusion criteria.

Subjects are included in the study if they meet all of the following criteria:

- Written informed consent provided by the patient
- Age ≥ 18 years
- Chronic Atopic Dermatitis present for at least 3 years
- Disease is not responsive to topical medications, or for whom topical treatments are not indicated or desired
- Willing and able to comply with all clinic visits and study-related procedure
- EASI score ≥ 16 at screening and baseline visits
- IGA score \geq 3 at screening and baseline visits
- $\geq 10\%$ body surface area (BSA) of AD involvement at screening and baseline visits
- Documented recent history (within 6 months before the screening visit) of inadequate response to treatment with topical medications or for whom topical treatments are otherwise medically inadvisable or undesired

Exclusion Criteria:

Subjects with ANY of the following will be excluded from the study:

- Treatment with an investigational drug within 8 weeks of baseline visit
- Having received the following treatments within 4 weeks before the baseline visit, or any condition that, in the opinion of the investigator, is likely to require such treatment(s) during the first 4 weeks of study treatment:

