3. STUDY DESIGN AND OBJECTIVES

Phase 2, open label, dose escalation study of two dose cohorts of bermekimab in patients with moderate to severe atopic dermatitis. The study is multicenter, and will consist of two dose levels: Bermekimab administered subcutaneously at a dose of 200 mg weekly (4 doses) and bermekimab administered subcutaneously at a dose of 400 mg weekly (8 doses). Patients taking the 200mg dose will be followed for 5 weeks (6 visits, day 35 ± 20 , and patients taking the 400mg dose will be followed for 8 weeks (9 visits, day 56 ± 20) to allow for assessment of safety and preliminary efficacy.

Dose escalation details can be found in Section 5.3.

The protocol of the study will be approved by the Institutional Review Board (IRB) or the Ethics Committee (EC) of the participating study sites. Depending on the participating countries, both local and central IRB/EC approvals will be granted. The study will be registered at www.clinicaltrials.gov before the enrollment of the first patient. The trial will be conducted in compliance with the protocol, GCP, and all applicable regulatory requirements.

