3.1 STUDY ENDPOINTS

Primary Endpoint:

• Safety and Tolerability

Secondary Endpoints:

- Change in Eczema Area and Severity Index Score (EASI) from baseline to visit 8 EASI score will assess severity and extent of AD with respect to erythema, excoriation, infiltration and lichenification at 4 anatomic sites of the body: lower and upper extremities, trunk and head. The total EASI score shall be in a range (from 0 to 72 points (from no disease to maximum disease severity, respectively).
- Patients (%) achieving Investigator's Global Assessment (IGA) Response (0 or 1) at Visit
 - 8

IGA assesses disease severity and clinical response using a 5-point scale: 0 = clear; 1 = almost clear; 2 = mild; 3 = moderate; 4 = severe. The score is determined by ranking the extent of erythema and papulation/infiltration. A clinical response to therapy will be an IGA score of 0 (clear) or 1 (almost clear). Patients receiving more than one treatment with additional medication to treat AD exacerbation during the study or missing IGA scores at Visit 8 will be treated as non-responders.

- Patients (%) achieving ≥2 IGA Score Reduction at Visit 8
- Pharmacokinetics (PK) Assessment

An enzyme-linked immunosorbent assay (ELISA) has been developed to specifically measure bermekimab levels in human plasma. Blood will be drawn into a single 6 ml Na-Heparin collection tube at each PK collection time point (sample collection is pre-dose at visit 1, visit 3, visit 5, and visit 8). These samples will be collected per the study lab manual and immediately shipped to the Sponsor for PK analysis. The PK samples will also be used to test for the presence of antibodies against bermekimab.

- Change (%) for peak weekly averaged pruritus numerical rating scores (NRS) from baseline to visit 8
- The NRS rating system captures the intensity of patient's itch and pain over a 24-hour period. The following question will be presented to patients: "how would a participant rate his or her itch at the worst moment and on average during the previous 24 hours (scale 0 10 [0 = no itch; 10 = worst possible itch])?" and "how would you rate your pain on average during the previous 24 hours [0 = no pain; 10 = severe pain])?

```
CONFIDENTIAL
```

- Change in weekly averaged peak NRS from baseline to visit 8
- Change in SCORing Atopic Dermatitis (SCORAD) score from baseline to visit 8
 SCORAD was developed by the European Task Force on Atopic Dermatitis

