 (Severity scoring of atopic dermatitis: the SCORAD index) as a measure of
 disease severity in AD. It includes assessment of the eczema in addition to patient
 reported symptoms. Total score ranges from 0 to 103 (no disease to most severe
 disease, respectively).
- Patients (%) achieving 50% or greater reduction in EASI Score from baseline to Visit 8
- Patients (%) achieving 50% or greater reduction in SCORAD Score to Visit 8
- Change (%) in Patient Oriented Eczema Measure (POEM) Scores from baseline to Visit 8
 POEM is a 7-item is a patient reported quality of life outcome measure based on a
 questionnaire to determine disease symptoms, including bleeding, cracking,
 dryness, flaking, itching, sleep loss and weeping. The scoring range is from 0 to
 28 (no disease to most severe disease, respectively).
- Changes in Global Individual Signs Score (GISS) from baseline to visit 8
 - GISS assesses AD lesions for erythema, excoriations, lichenification and edema/papulation. Each component will be rated on a global basis (over the entire body surface rather than by region) using a 4-point scale (0=none, 1=mild, 2=moderate and 3=severe) according to the EASI grading severity. Total score will range from 0 to 12 (no disease to most severe disease, respectively).
- Change from baseline to visit 8 in Dermatology Life Quality Index (DLQI)
- Change from baseline to visit 8 in Hospital Anxiety Depression Scale (HADS)
- Change (%) from pre- and post- injection of Visit 1 Questionnaire for pruritus, pain and erythema

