10.5 STATISTICAL METHODS

All analyses will be summarized using descriptive statistics and data will be presented in tabular format for each treatment group and pooling all bermekimab dose groups together. Continuous data will be summarized for each treatment group using the number of observations available (N), means, standard deviation (SD), minimums, medians, and maximums. Categorical data will be summarized for each treatment group using counts and percentages. Missing data will not be categorized in the summaries.

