10.5.4 Efficacy Analysis

All primary and secondary efficacy analyses will be performed for SAF and PP populations. Summary statistics will be provided to evaluate the overall treatment effect and effect within the treatment group. No statistical comparison of differences will be performed across bermekimab dose groups.

Change from baseline to visit 8 will be summarized using descriptive statistics. Corresponding 95% confidence interval of the point estimate of mean change will be provided by treatment group and for overall pooled population. The number and percent of subjects achieving the response (as specified for the secondary endpoints) will be summarized by treatment groups and overall population along with 95% confidence interval for the point estimate. Number and percent of patients achieving response in EASI, and SCORAD core from baseline at visit 8, will be reported separately, along with 95% confidence interval for 50% or greater reduction.

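### Group A is followed only to visit 6 in Section 3, yet its efficacy endpoints, per-protocol set, pooled summaries and only post-baseline ECG are placed at visit 8

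*Combined protocol and SAP*

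**What the plan says.** Section 3 sets follow-up by dose: "Patients taking the 200mg dose will be followed for 5 weeks (6 visits, day 35", while the 400 mg group has 9 visits, to day 56. The synopsis assigns 9 patients to Group A (200 mg, four doses) and 20 to Group B (400 mg, eight doses). For Group A it says: "Dosing will occur weekly from visit 1 to visit 4".

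The rest of the schedule makes no split by group. The synopsis duration, Section 2.9, the visit list in 5.1, the calendar in 5.2 and the adverse event window in 9.3 all run to the end of the eight-week schedule (visit 9). The patient diary covers days 0 to 35 in Section 5.1 but days 0 to 56 in Section 8.2.

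The analysis is fixed at visit 8 (day 49 ± 2):

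- Section 10.3.1: "The per protocol population will consist of those patients that complete both the baseline and visit 8 assessments of their atopic disease".
- Section 3.1, under IGA 0/1: patients with "missing IGA scores at Visit 8 will be treated as non-responders".
- Section 3.1 also lists "Patients (%) achieving 50% or greater reduction in EASI Score from baseline to Visit 8", with no missing-data rule. The same is true of the SCORAD 50% endpoint and the IGA reduction of at least 2 points.
- Section 10.5: "data will be presented in tabular format for each treatment group and pooling all bermekimab dose groups together".
- Section 10.5.4: "Corresponding 95% confidence interval of the point estimate of mean change will be provided by treatment group and for overall pooled population".

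Section 10.5.1 deals only with a missing baseline. ECG is scheduled at visits 1 and 8 only (5.1, 5.2). Section 7 counts it as a safety assessment, and 10.6.2 summarises it by treatment group.

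**The concern.** On Section 3's schedule, Group A leaves the study before the visit at which its efficacy is to be measured, and no other efficacy visit is named for it. The 200 mg rows would then be empty or produced by a missing-data rule, and the rows labelled as pooled would be Group B alone or a diluted Group B rate.

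On the unsplit calendar, Group A does reach visit 8, but four weeks after its last stated dose, so pooling combines patients at very different times since dosing.

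Section 1.2 describes the work as dose ranging to support later randomized studies. The by-group and pooled summaries are the study's whole efficacy output. The ECG gap matters separately, because safety and tolerability is the primary endpoint.

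**Working it through.** **1. Visit days.** In the 5.2 calendar, nominal day = 7 × (visit − 1). Visit 6 is day 35 and visit 9 is day 56, which reproduces Section 3's pairs of 6 visits/day 35 and 9 visits/day 56. Visit 8 is day 49. With the ± 2 day windows, visit 6 is at latest day 35 + 2 = 37 and visit 8 at earliest day 49 − 2 = 47, so a visit 6 assessment cannot serve as visit 8. The text of Section 3 prints a window of ± 20 days, probably a PDF reading fault. Even read literally (days 15 to 55), it still gives Group A only 6 visits.

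**2. Endpoints.** The synopsis and Section 3.1 each list 14 secondary endpoints. PK and the Visit 1 Questionnaire are not set at visit 8, which leaves 12: eight change scores (EASI, two NRS, SCORAD, POEM, GISS, DLQI, HADS) and four responder rates (IGA 0/1, IGA reduction ≥2, EASI-50, SCORAD-50).

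**3. If Section 3 governs.** Total N = 9 + 20 = 29.

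- Per-protocol set: Group A 0 of 9.
- Change scores: Group A N = 0; pooled N at most 20 of 29, all from Group B.
- IGA 0/1, missing-score rule read literally: Group A 0/9, Clopper-Pearson 95% CI 0 to 33.6% (illustrative, since the plan names no interval method). With x responders among 20 in Group B, the pooled rate is x/29, which is 20/29 = 0.69 of Group B's rate. If the rule covers only scheduled assessments that were missed, Group A has no rate and the pooled rate is x/20.
- The other three responder rates have no stated denominator. Assuming all 20 Group B patients are assessed:

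| Assumed Group B responders | Denominator 20 | Denominator 29 | Gap (points) |
|---|---|---|---|
| 4 | 20.0% | 13.8% | 6.2 |
| 8 | 40.0% (CI 19.1 to 63.9) | 27.6% (CI 12.7 to 47.2) | 12.4 |
| 12 | 60.0% | 41.4% | 18.6 |
| 16 | 80.0% | 55.2% | 24.8 |

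- Calendar assessments falling within screening to visit 6: post-baseline ECG 0 of 1; urinalysis 2 of 3 (last on day 21); chemistry/hematology 3 of 4 (last on day 28); PK and anti-drug antibody 3 of 4 (last on day 28).

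**4. If the calendar governs visits and the synopsis governs dosing.** Group A's last dose is at visit 4, day 21. Efficacy scores are taken before any injection at the visit.

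| Visit | Group A, days since last dose | Group B, days since previous dose |
|---|---|---|
| 5 (day 28) | 28 − 21 = 7 | 28 − 21 = 7 |
| 6 (day 35) | 35 − 21 = 14 | 35 − 28 = 7 |
| 8 (day 49) | 49 − 21 = 28 | 49 − 42 = 7 |

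These are nominal days. With ± 2 days at each visit, 28 becomes 24 to 32 and 7 becomes 3 to 11.

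**The case against.** The strongest points on the other side are these.

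- **The calendar does not by itself give 28 days.** Sections 5.1 and 5.2 mark an injection at visits 5 to 8 with no group split. Taken literally, that gives 7 days in both groups. This is correct, and the 28-day figure needs the synopsis dosing. But the literal reading contradicts the four doses stated in the synopsis and Section 3, so it adds a conflict to be reconciled and resolves none.
- **The 0/9 figure treats a visit that was never scheduled as a missing score.** That is a strained reading. The alternative leaves Group A with no IGA 0/1 result at all.
- **Section 10.5 implies available cases.** It says: "Continuous data will be summarized for each treatment group using the number of observations available (N". This reasonably settles N for the change scores. It does not fix the denominator of the three responder percentages.
- **Most of the safety shortfall is not a real loss.** Visit 5 laboratory and PK samples already follow Group A's fourth dose, and vital signs continue at every visit. This stands; only the ECG gap is substantive.
- **Everything affected is descriptive.** The primary endpoint has no hypothesis test, no comparison across doses is planned, and escalation uses the week 4 visit. This limits severity, but the affected rows would still be empty or misleading.
- **A later SAP could set group-specific visits.** Section 10 calls itself only the basis for one. A SAP could define analysis visits, but it cannot settle the protocol's visit schedule or ECG timing.

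**Conclusion.** The concern holds and should be fixed before analysis. Under Section 3, the rules as written give Group A a per-protocol set of 0/9, change scores with N = 0, an IGA 0/1 rate that is a forced 0/9 or absent, and no post-baseline ECG. The pooled row is then Group B alone (at most 20 of 29) or Group B's rate multiplied by 0.69. Under the calendar with four doses in Group A, the pooled visit 8 row mixes nominal gaps of 28 and 7 days since dosing.

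The counts rest on the planned group sizes. The 6.2 to 24.8 point range rests on assumed Group B results of 4/20 to 16/20 with no dropout. No error rate or power is affected, because none is planned, and Group B's own visit 8 results stand.

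**What to change.** 1. **Reconcile the schedule** across the synopsis, Sections 2.9, 3, 5.1, 5.2, 7, 8.2 and 9.3. Include the diary range, the ungrouped injection marks at visits 5 to 8, and which safety assessments apply to Group A. State whether Group A has a post-baseline ECG and at which visit; if it has none, say so in the 10.6.2 summary.
2. **Define the efficacy analysis visit by group** in the synopsis, 3.1, 10.3.1, 10.5.1 and 10.5.4. Tie the per-protocol set and the missing-IGA rule to each group's own visit. Add a missing-visit rule for IGA reduction ≥2, EASI-50 and SCORAD-50.
3. **Pool only where time since dosing is comparable.** Visit 5, pre-injection, qualifies on every reading of the schedule: nominally 7 days after the fourth weekly dose in both groups, with all eight efficacy instruments collected. Visit 6 is an alternative, but at 14 days against 7. State which is used and why.
4. **Report visit 8 by group without a pooled row.** If Group A is assessed there after four doses, label its values as 28 days after the last dose.
5. **Date the change** and state which efficacy data had been seen, since the trial is open label.

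Cost: the efficacy part is wording in five places and uses assessments already scheduled. The schedule part is a protocol amendment under Section 11.3. If Section 3 is kept, a post-baseline ECG in Group A would be an added assessment. Pooled figures would describe day 28 and say nothing about Group B's later doses, which remain in its visit 8 summary. Pooling at visit 5 still combines two dose levels.

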refrigeration and lay flat; allow to warm to room temperature. Do not heat

Pre-injection

- Concomitant medications/treatments
- o DLQI
- Urine pregnancy
- o EASI
- o IGA
- HADS
- Pruritus/Pain NRS: data from patient diary to be recorded at this time if available
- o SCORAD
- o POEM
- o GISS
- Vital signs (blood pressure, pulse, oxygen saturation, respiratory rate and body temperature)

Bermekimab subcutaneous injection in accordance with injection site determined by BMI at Screening

Post bermekimab subcutaneous injection

- 1 hour monitoring post-injection
 - Injection reaction
 - Vital signs (blood pressure, pulse, oxygen saturation, respiratory rate and body temperature) one hour post injection (70 +/- 10 minutes)
- Adverse event monitoring

Visit 8 (day 49 +/- 2)

> *At least 45 minutes before injection*: When using pre-filled syringes, remove syringe from

refrigeration and lay flat; allow to warm to room temperature. Do not heat

Pre-injection

- Concomitant medications/treatments
- Urinalysis
- Electrocardiogram (ECG) (patient should be supine for at least 5 minutes prior to performating ECG)
- Physical Examination
- o DLQI
- Urine pregnancy
- o EASI
- o IGA
- o HADS
- Pruritus/Pain NRS: data from patient diary to be recorded at this time if available
- o SCORAD
- o POEM
- o GISS
- Blood draw:
 - chemistry and hematology, 12.5mL
 - PK and Biomarker Analysis, 6mL
- Vital signs (blood pressure, pulse, oxygen saturation, respiratory rate and body temperature)

Bermekimab subcutaneous injection in accordance with injection site determined by BMI at Screening

Post bermekimab subcutaneous injection

- ➤ 1 hour monitoring post-injection
 - Injection reaction
 - Vital signs (blood pressure, pulse, oxygen saturation, respiratory rate and body temperature) one hour post injection (70 +/- 10 minutes)
- Adverse event monitoring

Visit 9 (56 +/- 2)

- Concomitant medications/treatments
- > DLQI
- Physical Examination
- ► EASI
- ► IGA
- > HADS
- > Pruritus/Pain NRS: patient diary to be retained and data to be recorded
- > SCORAD
- > POEM
- ➢ GISS
- Vital signs (blood pressure, pulse, oxygen saturation, respiratory rate and body temperature)
- Adverse Event Monitoring

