10.4 PATIENT DISPOSITION

A listing of all patients prematurely discontinued from the study, along with reasons for discontinuation will be provided. In addition, the total number of patients for each of the following categories will be summarized.

- The total number of screened patients: met the inclusion criteria regarding the target indication and signed the informed consent
- The total number of enrolled patients: met all inclusion/exclusion criteria and receive at least one dose of therapy
- The analysis sets (SAF, PP)
- The total number of patients who discontinued the study, and the reasons for discontinuation

• A listing of patients prematurely discontinued from treatment, along with reasons for discontinuation

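### The per protocol analysis of the Visit 1 Questionnaire, a day-0 outcome, is restricted to patients assessed at day 49, and read literally the rule leaves Group A with no per protocol patients

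*Combined protocol and SAP*

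**What the plan says.** Section 10.3.1 sets up two populations. For the first, "The safety analysis set (SAF) consists of all patients that receive at least one dose of study medication". For the second, "The per protocol population will consist of those patients that complete both the baseline and visit 8 assessments of their atopic disease", with the bracketed qualifier "as specified for the secondary endpoints". Section 10.5.4 then says: "All primary and secondary efficacy analyses will be performed for SAF and PP populations". Section 10.4 lists the SAF and PP among the patient totals to be summarised, without a separate count per endpoint.

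The secondary endpoints in Section 3.1 include "Change (%) from pre- and post- injection of Visit 1 Questionnaire for pruritus, pain and erythema". Under Section 5.1, Part 1 is completed before the first injection and Part 2 about an hour after it (70 ± 10 minutes), both at Visit 1. Visit 8 is day 49 ± 2.

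Section 3 follows Group A for six visits, to day 35, and Group B for nine visits, to day 56. The visit list in 5.1 and the calendar in 5.2 run to Visit 9 without separating the groups.

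Two other rules bear on the point. Section 10.5 summarises continuous data on the observations available. Section 3.1 counts a missing visit 8 IGA as non-response.

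**The concern.** An analysis set for an outcome measured on day 0 should not depend on what happens to the patient afterwards. Here it does: being assessed at day 49 decides who is counted for a change that was complete on the day of the first injection.

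The plan contains a route by which the two could be linked. Section 5.5 stops therapy for severe injection site reactions and for certain related adverse events. It does not require those patients to return for visit 8, and Section 9.3 provides for patients who leave the study early. A patient with a poor first experience could therefore be missing from the PP summary of that same experience.

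For the remaining endpoints the stake is reproducibility. The PP sentence does not say which instruments count, or whether membership is decided once or endpoint by endpoint. Two statisticians could build different PP sets from it, and in an open-label study that choice might be made after results are known. In addition, if Group A has no visit 8, its PP tables are empty and the pooled PP column is Group B alone.

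**Working it through.** **Inputs.** Group sizes of 9 and 20, total 29 (Synopsis). Six visits for Group A and nine for Group B (Section 3). Visit 8 at day 49 (5.1, 5.2). PP rule (10.3.1) and its use (10.5.4). The sample size is one of convenience (10.2), so there is no power calculation to reproduce, and the documents give no missing-data rate.

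**Stated figures.** 9 + 20 = 29, which agrees with the total. 49 / 7 = 7 weeks from the first injection to visit 8.

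**Visit 1 Questionnaire.** The outcome needs Part 1 and Part 2 only. There are two ways to apply the PP rule:
- One common list: a patient counts only if assessed at baseline and at visit 8, so the day-0 result is conditioned on day 49.
- Endpoint by endpoint: this endpoint has no visit 8 value, so its PP set is undefined.

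Neither reading gives a sensible set.

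**Group A.** Six visits means no visit 8. A literal PP contains 0 of 9 Group A patients, so its maximum is 29 − 9 = 20, and 20 / 29 = 69%, before any dropout.

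**Other endpoints (illustration only).** Suppose each required assessment is missing independently with probability q, and k assessments are required. The expected Group B PP size is then 20 × (1 − q)^k. The strictest reading takes eight instruments (EASI, IGA, SCORAD, NRS, POEM, GISS, DLQI, HADS) at two visits, so k = 16. An endpoint-specific set has k = 2. The values of q are assumptions.

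| Assumed q | (1 − q)^16 | Of 20, one list | (1 − q)^2 | Of 20, per endpoint |
|---|---|---|---|---|
| 1% | 0.851 | 17.0 | 0.980 | 19.6 |
| 2% | 0.724 | 14.5 | 0.960 | 19.2 |
| 5% | 0.440 | 8.8 | 0.9025 | 18.1 |

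This is close to a worst case. The instruments are completed at the same visits, so most missing data would come from whole missed visits. That positive correlation would shrink the gap between the columns.

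**The case against.** **The SAF analysis is intact.** Every secondary endpoint is also analysed on the SAF, which requires only one dose. The unconditioned Visit 1 result will therefore be reported. This stands, and it limits the consequence.

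**This PP is in effect a completer set.** A difference between SAF and PP that reflects retention is then what it is meant to show. That is fair for visit 8 endpoints. It gives no reason to apply the set to a same-day measure.

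**The bias may be negligible.** Section 9.7 reports injection site or infusion reactions in 20 of 831 patients, and all but two of those were grade 1 or 2 without discontinuation. Applied to this trial, 2 / 831 × 29 = 0.07 patients. Patients may leave for other reasons, so this is not a bound. It does mean that a reader who infers that the acute response will look better in PP than it was goes further than the documents allow.

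**The strict one-list reading is not the text.** A reader might infer that one missing questionnaire removes a patient from every endpoint. Section 10.3.1 does not say that all assessments are required, and its bracket can be taken endpoint by endpoint. HADS and DLQI, described in 8.2 as measures of mood and quality of life, are not plainly assessments of atopic disease. Even on the strict reading only the PP analyses are affected. Nor does the diary instruction "data from patient diary to be recorded at this time if available" help that inference: it concerns when sites transcribe entries, and nothing says that one missing daily entry voids a weekly average or ends PP membership.

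What supports the one-list reading is the single PP total in 10.4. Also, because 10.5 already uses available observations, a per-endpoint PP would add little for change scores. The wording is ambiguous, and that ambiguity is all that can be claimed.

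**Everything is descriptive.** No formal test is planned for the primary endpoints, and the dose groups are not compared. This stands and lowers the stakes further.

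**Conclusion.** The point holds for the Visit 1 Questionnaire. As written, its PP analysis is selected on assessment seven weeks after the outcome. It loses anyone who left after the first injection and, taking Section 3 literally, all 9 Group A patients, so it can include at most 20 of 29. That cap assumes Group A really has no visit 8; the undivided schedule in 5.1 and 5.2 leaves this to be reconciled. The direction of any bias is plausible but not shown, and the SAF result for the endpoint is sound.

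For the other secondary endpoints the finding is an ambiguity and not a demonstrated loss. If PP were one list requiring every instrument, one missing form would cost a patient all PP analyses, but no SAF analysis. The Group B figures (17.0, 14.5 or 8.8 patients against 19.6, 19.2 or 18.1) rest on assumed, independent missingness and should be read only as an upper illustration of that loss. This is worth correcting because the correction is nearly free; the trial's main conclusions do not depend on it.

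**What to change.** In Section 10.3.1:
- For the Visit 1 Questionnaire, include all dosed patients with both Part 1 and Part 2, and drop the visit 8 requirement.
- For each other visit 8 endpoint, define PP as patients with the baseline and visit 8 values of that endpoint.
- Reconcile the visit 8 requirement with Group A's six-visit follow-up in Section 3 and with the schedule in 5.1 and 5.2, and state which assessment the Group A analysis uses. Without this step the per-endpoint definition still leaves Group A empty at visit 8.

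In Section 10.4, report the PP count per endpoint, and show the n in every PP table.

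The cost is a few sentences. The PP n will differ between endpoints. For change scores, PP will largely coincide with the SAF available-case result. For IGA response the two can still differ, because a missing visit 8 score counts as non-response in the SAF.
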